9.1 Efficacy Assessments

9.1.1 *Tumor Assessment*

Initial (screening) tumor assessments must be performed within 28 days prior to the first dose of study treatment. The investigator/site radiologist must review pre-trial images to confirm the patient has measurable disease per RECIST 1.1 ([Appendix B: Tumor Assessment Criteria](#)). Tumor assessments performed as standard of care prior to obtaining informed consent and within 28 days of the first dose of study treatment may be used rather than repeating tests. Beginning with screening, all imaging assessments will be evaluated using RECIST 1.1. On-study imaging assessments will be performed every 6 weeks (Q6W) calculated from the date of therapy initiation and independent of treatment delays. RECIST 1.1 will be used by the site for treatment decisions until the first radiologic evidence of progressive disease (PD). The Sponsor may request digitized scans from patients to confirm response.

Following the first radiologic evidence of PD by RECIST 1.1, treatment decisions may be made by using immune iRECIST ([Appendix B: Tumor Assessment Criteria](#)) to accommodate tumor response patterns seen with CPI therapy including pembrolizumab treatment (e.g., tumor flare). This was described by Nishino, et al. 2016 [\[13\]](#) and is used in immunotherapy clinical trials. For a clinically stable subject with first radiologic evidence of PD, it is at the discretion of the site investigator to continue treating the subject with SNS-301 and pembrolizumab until PD is confirmed at least 4 weeks after the date of the first tumor imaging suggesting PD per the site investigator. If radiologic PD is confirmed by the subsequent tumor imaging, the subject should be discontinued from treatment unless, in the opinion of the investigator, the subject is achieving a clinically meaningful benefit. In this case, an exception for continued treatment may be considered following consultation with the Sponsor. Additional treatment response evaluation by RECIST v 1.1 and iRECIST may be performed at the Sponsor's discretion.

Patients will undergo tumor assessments every 6 weeks (± 7 days) until approximately 12 months following first dose of study treatment, or earlier if clinically indicated. After 12 months, tumor assessments will be required every 12 weeks (± 7 days). Imaging should continue to be performed until disease progression is assessed by the Investigator, the start of new anti-cancer treatment, withdrawal of consent, death or the end of the trial, whichever occurs first for efficacy follow-up. Patients who start a new anti-cancer therapy will be censored for survival and progression analyses at date of last scan prior to the start of new anti-cancer therapy.

Tumor imaging should be performed by computed tomography (CT), but may be performed by magnetic resonance imaging (MRI) if CT is contraindicated, but the same imaging technique should be used in patient throughout the trial. CT scans (with oral/IV contrast unless contraindicated) must include chest, abdomen and pelvis. The investigator must review before dosing at the next visit. Per RECIST 1.1, response should be confirmed by a repeat radiographic assessment. The scan for confirmation of response may be performed no

earlier than 4 weeks after the first indication of response, or at the next scheduled scan, whichever is clinically indicated.

Patients who have unconfirmed disease progression may continue on treatment until progression is confirmed. If radiologic imaging by local/site assessment shows progressive disease (PD), tumor assessment may be repeated 4 weeks later in order to confirm PD with the option of continuing treatment per below while awaiting radiologic confirmation of progression. If repeat imaging shows SD, PR or CR, treatment may be continued as per treatment schedule. If repeat imaging still meets the threshold for PD ($\geq 20\%$ increase in tumor burden compared to nadir) but shows a reduction in tumor burden compared to the previous time point, treatment may be continued as per treatment calendar after consultation with Sponsor. If repeat imaging confirms progressive disease without reduction in tumor burden compared to the previous time point, patients will be discontinued from study treatment.

The decision to continue study treatment after the first evidence of disease progression is at the Investigator's discretion based on the clinical status of the patient as described in [Table3](#) below. Confirmatory imaging may be performed as early as 28 days later; alternatively, the scan performed at the next scheduled time point may be used as confirmation. Patients may receive study treatment while waiting for confirmation of PD if they are clinically stable as defined by the following criteria:

- Absence of signs and symptoms (including worsening of laboratory values) indicating disease progression
- No decline in ECOG performance status from baseline
- Absence of rapid progression of disease
- Absence of progressive tumor at critical anatomical sites (e.g., cord compression) requiring urgent alternative medical intervention
- Evidence of clinical benefit (defined as the stabilization or improvement of disease- related symptoms) as assessed by the investigator

Table 3: Imaging and Treatment after First Radiologic Evidence of Progressive Disease

	Clinically Stable		Clinically Unstable	
	Imaging	Treatment	Imaging	Treatment
1 st radiologic evidence of PD	Repeat imaging at ≥ 4 weeks at site to confirm PD	May continue study treatment at the Investigator's discretion while awaiting confirmatory scan by site	Repeat imaging at ≥ 4 weeks to confirm PD per physician discretion only	Discontinue Treatment
Repeat scan confirms PD (no reduction in tumor burden from prior scan)	No additional imaging required	Discontinue treatment	No additional imaging required	N/A

Repeat scan confirms PD (reduction in tumor burden from prior scan)	Continue regularly scheduled imaging assessments	Continue study treatment after consultation with Sponsor	Continue regularly scheduled imaging assessments	May restart study treatment if condition has improved and/or clinically stable per Investigator and Sponsor's discretion
Repeat scan shows SD, PR or CR	Continue regularly scheduled imaging assessments	Continue study treatment at the Investigator's discretion	Continue regularly scheduled imaging assessments	May restart study treatment if condition has improved and/or clinically stable per Investigator's discretion

Patients in whom radiographic disease progression is confirmed at a subsequent tumor assessment may be considered for continued study treatment at the discretion of the investigator if they continue to meet the criteria above and have evidence of the clinical benefit (see [Figure 2](#)).

[figure not shown]

Figure 2: Conditions for Continuing Study Treatment in the Presence of Increased Radiographic Tumor Size

Patients who discontinue from treatment for reasons other than disease progression (e.g., toxicity) will continue scheduled tumor assessments until disease progression, start of new-anti cancer therapy, withdrawal of consent, or death. Investigators may perform additional scans or more frequent assessments if clinically indicated. Patients who continue treatment beyond radiographic or clinical disease progression will be monitored with a follow-up scan at the next scheduled tumor assessment.

Imaging timing should follow calendar days and should not be adjusted for delays or changes in treatment administration dates.

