4. SNS-301 will be administered intradermally using the 3M micro-needle device. The dosing schedule will be as follows: Day 0, Week 3, Week 6, Week 9 then every 6 weeks (\pm 3 days) for 6 additional doses, thereafter every 12 weeks (\pm 3 days) until confirmed disease progression, unacceptable toxicity, deemed intolerable by the investigator or up to 24 months in patients without disease progression.
5. Pembrolizumab will be administered either every 3 weeks or every 6 weeks until confirmed disease progression, unacceptable toxicity, deemed intolerable by the investigator or up to 24 months in patients without disease progression.
6. Imaging will be performed at 6 weeks (\pm 7 days) calculated from the first dose and will continue to be performed every 6 weeks (\pm 7 days), for the first 54 weeks, or earlier if clinically indicated. Thereafter, imaging will be performed approximately every 12 weeks (\pm 7 days). Imaging timing should follow calendar days and should not be adjusted for delays or changes in treatment administration dates.
7. In patients who discontinue trial therapy for any reason other than radiologically defined confirmed progression, tumor imaging should be performed at the time of treatment discontinuation (\pm 4 weeks). If previous tumor imaging was obtained within 4 weeks prior to the date of discontinuation, then additional tumor imaging at treatment discontinuation is not required.
8. Patients will be followed for all adverse events (AEs) for 30 days and for adverse events of special interest (AESI) and serious adverse events (SAEs) occurring up until 90 days after the last dose of study treatment or until the start of a new anti-cancer treatment, whichever comes first. If the investigator becomes aware of an AESI or SAE that is considered related to study treatment after discontinuation from the trial, those events should be reported to the Sponsor within 24 hours.
9. All patients who experience disease progression, have unacceptable toxicity or start a new anti-cancer therapy and are discontinued from the trial will be followed for survival and subsequent anti-cancer therapy. Patients should be contacted (i.e. by telephone) every 3 months to assess for survival status for up to 3 years, until death or patient withdraws consent. A pregnancy test is also required for WOCBP every 3 months.

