9.2.14.6 Follow-Up

Survival follow-up information will be collected via telephone calls, patient medical records, and/or clinical visits approximately every 3 months for up to 3 years, until death, lost to follow-up, withdrawal of consent, or trial termination by Sponsor. All patients will be followed for survival and new anticancer therapy information unless the patient requests to be withdrawn from follow-up; this request must be documented in the source documents

and signed by the investigator. If the patient discontinues study treatment without documented clinical disease progression, every effort should be made to follow up regarding survival, progression (if not already progressed), and new anti-cancer therapy.

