10.4 Statistical Analyses

The statistical analysis plan will be developed and finalized before database lock and will describe the patient populations to be included in the analyses, and procedures for accounting for missing, unused and spurious data.

The statistical analysis plan will specify how lost to follow-up patients will be addressed in the primary analysis.

10.4.1 *General Methods*

All summarizations will be presented separately for each cohort, and over all subjects combined.

For continuous variables, descriptive statistics (number (n), mean, median, standard deviation, minimum and maximum) will be presented. For categorical variables, frequencies and percentages will be presented. For time-to-event variables, percentages of patients experiencing that event will be presented and median time-to-event will be estimated using the Kaplan-Meier method. As appropriate, a 95% CI will be presented. Graphical displays will be presented, as appropriate.

Patients demographic characteristics including age, gender, and race will be analyzed, with categorical variables summarized in frequency tables while continuous variables summarized using mean (standard deviation) and median (range).

All data collected will be presented in by-patient data listings.

10.4.2 *Efficacy Analyses*

ORR is defined as the proportion of patients with a confirmed best response of iCR or iPR by iRECIST. Objective response rate will be estimated, and 90% CI based on the exact binomial distribution will be presented by cohort and overall, including number and percent of patients in each overall response category.

The primary analysis will be based on objective response at Week 12. An additional analysis of ORR based on best objective response during the study will be performed.

DOR, DCR, PFS, and OS will also be calculated, defined as follows:

- DOR: time from date of first response to date of progression, where patients without progression are censored at date of last valid disease assessment
- DCR: proportion of patients with SD or better (PR and CR). SD for at least six months
- PFS: time from date of start of treatment to date of progression, where patients without progression are censored at date of last valid disease assessment
- OS: time from date of start of treatment to date of death or censored at date of last contact

Efficacy analyses will be performed using the efficacy-evaluable analysis set.

10.4.3 *Safety Analyses*

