#### Overall Survival (OS)

- OS is defined as time from date of start of treatment to date of death.
- OS rate at 12 weeks and the corresponding 95% CIs will be calculated and summarized based on Kaplan-Meier product limit estimates and will be displayed along with the corresponding number of subjects at risk.
- Subjects who are still alive will be censored on the date of last contact.
- The 25th percentile, Median, and 75th percentile of OS as well as the corresponding 95% confidence limits will be estimated using Kaplan-Meier method. Number of patients who died and number censored will be presented.
- Kaplan-Meier curves of OS by cohort will be displayed graphically.

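### Protocol 9.1.1 censors survival at the last scan before new anti-cancer therapy, which contradicts the OS definition in Protocol 10.4.2 and SAP 7.1

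*Protocol*

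**What the plan says.** Protocol 9.1.1, in the paragraph on how long imaging continues: "Patients who start a new anti-cancer therapy will be censored for survival and progression analyses at date of last scan" before the start of that therapy.

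Protocol 10.4.2 defines the endpoint without any exception for new therapy: "OS: time from date of start of treatment to date of death or censored at date of last contact".

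SAP 7.1 agrees with 10.4.2. "OS is defined as time from date of start of treatment to date of death", and "Subjects who are still alive will be censored on the date of last contact".

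Follow-up is set up to match the last two. Item 9 of the synopsis procedures says that patients who "start a new anti-cancer therapy and are discontinued from the trial will be followed for survival and subsequent anti-cancer therapy". Protocol 9.2.14.6 sets contacts "approximately every 3 months for up to 3 years, until death, lost to follow-up, withdrawal of consent, or trial termination by Sponsor".

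For progression, Protocol 10.4.2 censors PFS and DOR at the last valid disease assessment. SAP 7.1 uses the last tumor assessment and adds rules for patients with no assessment and for those who discontinue or withdraw. Neither section says what happens when a new anti-cancer therapy starts.

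**The concern.** The protocol contains two OS censoring rules that cannot both be applied. Under 9.1.1 a patient who switches therapy leaves the OS analysis at an earlier scan. Under 10.4.2 and the SAP that patient stays in until death or last contact.

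OS is listed among the primary anti-tumor endpoints in Protocol 4.2.1, and SAP 7.1 plans Kaplan-Meier quartiles, a 12-week rate and curves by cohort. New therapy usually follows progression, so censoring at the scan before it removes patients at about the time their risk of death changes. Kaplan-Meier estimation assumes that censored patients have the same future risk as those who remain, and here they would not.

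The trial is open-label. If the choice of rule stays open, it could be made after outcomes are known.

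**Working it through.** **Text comparison.** Take a hypothetical patient whose week 12 scan shows progression, who then starts a new therapy and who dies within the 3-year follow-up.

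| Source | OS outcome for this patient |
|---|---|
| Protocol 9.1.1 | Censored at the week 12 scan |
| Protocol 10.4.2 | Event at date of death |
| SAP 7.1 | Event at date of death |
| Synopsis item 9; Protocol 9.2.14.6 | Death is collected |

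The same patient exposes a second fault. Read literally, 9.1.1 also censors the progression analysis at the week 12 scan, which is the scan that documents progression. A PFS event becomes a censored time.

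**Plan's own figures.** The documents state no OS figure, so there is none to reproduce. The stated design figures concern objective response. With n1 = 15, n = 30, continuation at r1 or more responses and rejection at r or more:

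P(reject) = Σ over x from r1 to 15 of P(X1 = x) × P(X2 ≥ r − x), with X1 and X2 each binomial(15, p).

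- Cohort A (r1 = 1, r = 4, p = 5% v 18%): type I error 5.8% (stated 6%), power 80.0% (80%), early stopping under the null 0.95^15 = 46.3% (46%).
- Cohort B (r1 = 2, r = 7, p = 13.3% v 29%): 9.2% (9.2%), 80.1% (80.1%), early stopping 38.8% (38.8%).

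All agree after rounding, and no survival quantity enters them.

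**Illustration of size if 9.1.1 were applied to OS.** Every clinical input here is assumed except the 3-year follow-up and the cohort size of 30. Times are exponential:

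- median time to progression 3 months
- median time to death without progression 24 months
- median survival after progression 4, 6 or 8 months, the same for switchers and non-switchers
- 20%, 40% or 60% of progressors alive one month later start a new therapy, and their last scan is the progression scan
- follow-up 36 months

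Each cell shows the value with censoring at last contact, then the value under 9.1.1.

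| Median survival after progression | Share switching | Deaths counted per 30 | Median OS (months) | 12-month OS |
|---|---|---|---|---|
| 4 | 20% | 29.8 → 25.4 | 7.3 → 7.5 | 26% → 27% |
| 4 | 40% | 29.8 → 21.0 | 7.3 → 7.7 | 26% → 29% |
| 4 | 60% | 29.8 → 16.5 | 7.3 → 8.0 | 26% → 30% |
| 6 | 20% | 29.3 → 24.7 | 9.2 → 9.3 | 37% → 38% |
| 6 | 40% | 29.2 → 20.0 | 9.2 → 9.5 | 37% → 39% |
| 6 | 60% | 29.2 → 15.5 | 9.2 → 9.8 | 37% → 40% |
| 8 | 20% | 28.2 → 23.7 | 10.9 → 10.9 | 46% → 46% |
| 8 | 40% | 28.2 → 19.2 | 10.9 → 11.2 | 46% → 47% |
| 8 | 60% | 28.2 → 14.7 | 10.9 → 11.4 | 46% → 48% |

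Deaths lost run from 29.8 − 25.4 = 4.4 to 29.2 − 15.5 = 13.7. Median OS rises by 0 to 0.7 months and 12-month OS by 0 to 4 points.

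**Direction.** The rise depends on the equal-survival assumption. A second version drops death without progression and keeps the one-month delay. With equal medians of 4 to 6 months and 30% to 60% switching, median OS rises by 0.5 to 1.5 months. With a post-progression median of 8 months for switchers and 3 for non-switchers, it falls: from 8.4 to 8.0 months at 30% switching, and by about half a month from 10.0 at 60%. Censoring the longer survivors leaves the worse-prognosis progressors at risk and pulls the curve down.

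**The case against.** The strongest reply is that the two sections that define OS are both sound. SAP 7.1 is written against Protocol Version 4.0 and is to supply the results for the study report. If analysts follow it, no death after a switch is dropped. That stands: the loss occurs only if 9.1.1 is applied over 10.4.2 and the SAP. It does not remove the conflict. SAP Section 1 says that the SAP sets out its differences from the protocol's planned methods, yet the SAP neither adopts the 9.1.1 rule nor lists it as a departure.

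A second reply is that the 9.1.1 wording is a loose reference to progression-free survival. It sits among imaging rules and censors at a scan date, so this may be what was meant. The sentence does not say so, it names survival and progression as separate analyses, and the protocol writes PFS out in full elsewhere. If PFS was intended, the wording still needs correcting.

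Third, OS has no hypothesis and no decision rule in this trial. That is correct, and it limits the consequence to descriptive estimates.

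A reader might also infer that OS will be biased upward, or that a set fraction of deaths such as 30% to 60% will disappear. The documents support neither. They give no switching rate, and the direction turns on who receives further therapy. Nor is every switcher a progressor, since the protocol allows patients to stop for toxicity and start another therapy.

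**Conclusion.** Wrong as written. The 9.1.1 sentence contradicts the OS definition in Protocol 10.4.2 and SAP 7.1, and it contradicts the survival follow-up that the protocol requires after new therapy. This conclusion rests on the text alone and needs no assumption.

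The consequence is conditional. If 9.1.1 governed OS, deaths after a switch would be discarded and the censoring would be informative. Under the assumed inputs that is roughly 4 to 14 of about 28 to 30 deaths per 30 patients, a large loss of events. The accompanying shift in median OS is at most about 1.5 months and of either sign.

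Post-switch deaths within follow-up are plausible. Protocol 3.3 cites median OS under 12 months for patients who do not respond to checkpoint inhibitors and under 6 months after progression on platinum as well. For single-agent pembrolizumab, the trial described in Protocol 3.2.1.1 gives 12.3 and 14.9 months in its two PD-L1-selected subgroups, nearer to the first-line part of Cohort B. All of these are well inside 3 years.

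The Simon stage rules and the sample size are unaffected.

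**What to change.** 1. In Protocol 9.1.1, remove *survival and* from the sentence, and limit what remains to PFS and DOR in patients with no documented progression before the new therapy. Deleting the two words alone is not enough, because the sentence would still censor a patient whose last scan already showed progression.
2. State that same new-therapy rule for PFS and DOR in Protocol 10.4.2 and SAP 7.1.
3. State in both places that OS counts all deaths regardless of subsequent therapy, with censoring only at last contact.
4. If an OS analysis censored at new therapy is wanted, add it as a labelled sensitivity analysis.

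The cost is a few sentences in each document. Protocol 11.1.1 requires IRB/IEC approval of amendments, so the protocol edit can go with the next one. The change needs no new data and does not alter sample size, follow-up or patient management.

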9.2 Safety Assessments

9.2.1 *Demographics and Medical History*

Demographics will include gender, year of birth, race and ethnicity.

Medical history will include details regarding the patients overall medical and surgical history as well as detailed information regarding the patient's previous treatment, including systemic treatments, radiation and surgeries, pathology, risk stratification, etc. since their original diagnosis. HPV status, EBV status and progression data will also be collected. Reproductive status and smoking/alcohol history will also be captured.

9.2.2 *Physical Examinations*

A complete physical exam will include, at a minimum head, eyes, ears, nose, throat and cardiovascular, dermatological, musculoskeletal, respiratory, gastrointestinal and neurological systems. Height (screening only) and weight will also be collected. Additionally, any signs and symptoms, other than those associated with a definitive diagnosis, should be collected at baseline and during the study.

During the study, a targeted, symptom-directed exam, as clinically indicated will be performed within 72 hours of each dosing visit

9.2.3 *Eastern Cooperative Oncology Performance Status*

The health, activity and well-being of the patient will be measured by the ECOG performance status and will be assessed on a scale of 0 to 5 with 0 being fully active and 5 being dead. Full details are described in [Appendix B: ECOG Performance Status](#). ECOG performance status will be collected within 72 hours of each dosing visit.

9.2.4 *Vital Signs*

Vital signs will include temperature, blood pressure, pulse rate and respiratory rate. For first infusion of pembrolizumab, the patient's vital signs should be determined within 60 minutes before the infusion. If clinically indicated, vital signs should be recorded at 15, 30, 45, and 60 minutes (\pm 5 minutes for all timepoints) after the start of the infusion, and 30 (\pm 10) minutes after the infusion. For subsequent infusions, vital signs will be collected within 60 minutes before the infusion and at 30 (\pm 5) minutes after the infusion.

Patients will be informed about the possibility of delayed post-infusion symptoms and instructed to contact their trial physician if they develop such symptoms.

9.2.5 *Electrocardiograms*

A 12-lead ECG will be obtained at screening and when clinically indicated. Patients should be resting in a supine position for at least 10 minutes prior to ECG collection.

9.2.6 *Clinical Safety Laboratory Assessments*

Hematological toxicities will be assessed in term of hemoglobin value, white blood cell, neutrophil, platelet and, lymphocyte count according to NCI-CTCAE V5.0 AE grading.

Laboratory abnormalities (grade 1 and greater that are listed in the NCI-CTCAE V5.0) should be recorded on the AE page regardless of their causality. Laboratory abnormalities associated with a definitive diagnosis will not be recorded as an AE unless it has become worse since baseline. Test analytes are provided in the table below.

See the Time and Events Schedule for timing and frequency. Safety labs will be performed within 72 hours of each dosing visit.

Hematology	Serum chemistry
Hematocrit (Hct)	Albumin
Hemoglobin (Hgb)	Alanine aminotransferase (ALT)
Platelet count	Aspartate aminotransferase (AST)
Red blood cell (RBC) count	Alkaline phosphatase (ALP)
White blood cell (WBC) count	Blood Urea Nitrogen (BUN) or Urea
Neutrophils	Bicarbonate or Carbon dioxide (CO ₂)
Lymphocytes	Creatinine
Eosinophils	Creatine phosphokinase (CPK)
Monocytes	Electrolytes (Na, K, Mg, Cl, Ca, P)
Basophils	Glucose (either fasting or non-fasting)
Other cells, if any	Lactate dehydrogenase (LDH)
Thyroid	Total bilirubin (direct bilirubin if elevated)
TSH, T3 and FT4	Total protein
Coagulation	Urinalysis
International normalized ratio/INR	Specific gravity
Activated partial thromboplastin time (PTT)	pH
Other anticoagulant monitoring (if required)	Glucose
HIV screen (at screening, if indicated)	Protein
Hepatitis screen (at screening, if indicated)	Ketones
HPV/EBV screen (at screening, if unknown)	Blood
Pregnancy test	Microscopic exam, if abnormalities

9.2.7 *Hepatitis and HIV Screening*

Patients should be tested for HIV locally prior to the inclusion into the trial only based on investigator's clinical suspicion for HIV infection and HIV-positive patients will be excluded from the clinical trial. Hepatitis B surface antigen, anti-HBc antibody, anti-HBs antibody, and Hepatitis C antibody immunoassays should be tested only per investigator's clinical suspicion during screening and tested locally. In patients who have positive serology for the anti-HBc antibody, HBV DNA should be tested prior to Day 0.

9.2.8 *Pregnancy Test*

A Serum pregnancy test (for women of childbearing potential, including women who have had a tubal ligation) must be performed and documented as negative within 72 hours prior to each dose.

9.2.9 *Urinalysis*

Urinalysis includes specific gravity, pH, glucose, protein, ketones, blood, and a microscopic exam if abnormal results are noted.

9.2.10 *TSH, T3 and FT4*

Thyroid function tests will be performed at screening and every 6 weeks thereafter.

9.2.11 *Creatine Phosphokinase (CPK)*

CPK will be performed at screening and at the discontinuation visit.

9.2.12 *HPV/EBV Testing*

If the patient's HPV/EBV status is unknown, they should be tested prior to receiving SNS-301. The results do not need to be known before the patient receives study treatment.

9.2.13 *PD-L1 Testing*

If the patient's PD-L1 status is unknown, they should be tested, preferably by 22C3 IHC. Patients who are CPI naïve must be PD-L1 positive prior to entry onto the study. For other patients, the results do not need to be known before the patient receives study treatment. If possible, for patients that started study treatment prior to Amendment 2/Version 3.0, retrospective testing should be done.

9.2.14 *Immunogenicity Assessments*

Detailed instructions on the collection and processing of immunogenicity samples will be located in the Laboratory Manual. See the Time and Events Schedule for a collection timeline for each sample.

9.2.14.1 *Blood Assays*

Blood assays include those measured in serum, plasma and whole blood/PBMCs.

9.2.14.1.1 *Serum and plasma*

Serum and plasma are collected for the direct measure of ASPH levels, anti-ASPH antibodies, anti-phage antibodies and other tumor biomarkers.

9.2.14.1.1.1 *ASPH*

Subject sera and/or plasma will be tested for the presence of ASPH and/or exosomes that contain ASPH on their surface by ELISA using several different monoclonal antibodies that are reactive with the ASPH protein. The presence of ASPH in serum or plasma is an indicator of cancer status. Alterations in ASPH levels may be indicative of response to treatment.

9.2.14.1.1.2 *Anti-ASPH antibodies*

Production of anti-ASPH antibodies is a direct result of an active immune response to the vaccine. Levels of anti-ASPH antibody are expected to rise during an active immune response and should reach a plateau level at maximal response. Continued and regular boosting of the vaccine during the course of treatment is expected to maintain or restore this level of anti-ASPH antibody in serum.

9.2.14.1.1.3 *Anti-phage antibodies*

Because the vaccine is delivered using a bacteriophage vector, production of anti-phage antibodies is also expected and is a direct result of an active immune response to the vaccine. High levels of anti-phage antibody may result in neutralization of further doses/boosts of vaccine. During the Phase I clinical study it was found that the use of a lower dose of vaccine during initial vaccination attenuate the production of anti-phage antibodies and this finding contributed to the selection of the dose for the current trial. Levels of anti-phage antibodies will be monitored here to ascertain if any correlation exists between the production of anti-phage antibodies and reduced efficacy of the vaccine.

9.2.14.1.1.4 *Other tumor and immune biomarkers*

Levels of other cancer biomarkers and cytokines may also be tested in serum and/or plasma and may also be used to monitor cancer status and response to treatment.

9.2.14.1.1.5 *Circulating tumor DNA (ctDNA)*

Blood samples will be collected in Streck tubes for isolation of ctDNA. ctDNA analysis may be used as a tool to monitor for treatment efficacy and resistance and for predicting the likelihood of relapse.

9.2.14.1.2 *Whole blood/ peripheral blood mononuclear cells (PBMCs)*

PBMCs are collected to monitor overall and specific immune responses.

9.2.14.1.2.1.1 *T-cells Evaluation*

T cell responses will be assessed using antigen-specific IFN- γ ELISpot assay using antigen presenting cells loaded with either full-length recombinant ASPH protein or overlapping peptide libraries covering the SNS-301 antigens. Antigen specific T cell responses may also be assessed via flow cytometry. Flow cytometric assays may include an examination of the influence of immunotherapy on the ability of patient T cells to exhibit phenotypic markers associated with cytolytic potential, activation or exhaustion after stimulation by peptides corresponding to SNS-301 antigens. Markers that may be used for this purpose include CD3, CD4, CD8, CD137, CD69, CD38, PD1, Granzyme A, Granzyme B and Perforin. These markers may change relative to new data becoming available that is informative for this assessment. Additionally, T-cell responses to general immune stimulators may be evaluated in order to track general cellular immune competence during the trial.

Additionally, ASPH-specific T-cells may be isolated, cloned and expanded *ex vivo*. For expansion antigen presenting cells loaded with either full-length recombinant ASPH protein or overlapping peptide libraries covering the SNS-301 antigens would be employed. These T-cells may be characterized by sequencing of their T-cell receptors (TCRs) to assess diversity and putative antigen specificity.

9.2.14.2 *Tissue*

A tissue sample is required at study entry. Ideally, a pre-treatment tissue sample obtained after initiation of ongoing CPI therapy and first dose of SNS-301 and pembrolizumab on this current clinical trial will be collected. Patients are requested to provide archival tissues from a prior biopsy or surgery that is treatment -naïve including prior 1) chemotherapy, radiation and 2) anti PD(L)-1 treatment-naïve, pending availability. In patients undergoing a pre-treatment biopsy, an archival tumor specimen, if available, should also be submitted. After signing of the Informed Consent Form, tumor tissue should be submitted to the Sponsor in a timely manner. All patients will undergo a mandatory tumor biopsy sample collection, if clinically feasible as determined by the trial investigator in consenting patients, at Week 6/3rd dose (+/- 3 days). Additionally, up to two optional biopsies may be obtained any time during the study, if medically feasible. A biopsy may also be obtained at the time of first evidence of radiographic or clinical disease progression. For patients who respond and subsequently progress, an optional biopsy may be obtained at the time of disease progression. Tumor tissue should be of good quality based on total and viable tumor content. Acceptable samples include core needle biopsies for deep tumor tissue or lymph nodes or excisional, incisional, punch, or forceps biopsies for cutaneous, subcutaneous, or mucosal lesions. Fine-needle aspiration may be acceptable pending sponsor approval however, brushing, cell pellets from pleural effusion, and lavage samples are not acceptable. For core needle biopsy specimens, at least three cores should be submitted for evaluation. Patients who are unable to undergo biopsy sample collection but otherwise meet criteria outlined in protocol may continue to receive study treatment.

If a tumor biopsy is to be obtained from an intended target lesion during eligibility assessment, the biopsy should be performed prior to obtaining the baseline scan. Otherwise, a new baseline scan should be obtained.

Archival and fresh tumor tissue samples should be representative tumor specimens in formalin-fixed paraffin embedded (FFPE) blocks (preferred) or at least 15 unstained slides, with an associated pathology report, should be submitted for intra-tumoral immunology assessments. Tissue slices of 4-5 microns are mounted on positively charged glass slides. Slides should be unbaked and stored cold or frozen.

9.2.14.2.1 *Tissue Assays*

Available tumor tissue collected from pre- and post- treatment may be assessed for the presence of immune cells using immunohistochemistry or immunofluorescence. The presence of immune signatures may also be analyzed through the assessment of various transcripts suggestive of an inflammatory or an immunosuppressive tissue microenvironment.

Tumor tissue will be collected for immunology assessments including but not limited to markers related to inflammation, suppression, T cell infiltration, and associated tumor microenvironment characteristics. Tumor infiltrating lymphocytes may be isolated and subjected to single cell expression profiling and/or TCR sequencing.

In addition, exploratory biomarkers may be evaluated.

9.2.14.2.2 *ASPH Immunohistochemistry (IHC) Assay*

ASPH testing will be done by immunohistochemistry on either fresh or archival tumor tissue. Samples will be analyzed at Fred Hutchinson Cancer Center via a CLIA validated assay.

9.2.14.3 *Future Biomedical Research*

The following samples are obtained as part of the study, if any leftover samples remain, they may be used for future biomedical research either during the course of the study or after the study has completed.

- Leftover tumor tissue
- Leftover RNA or DNA isolated from biological samples (blood, urine, tumor)

- Leftover biomarker samples (serum, plasma and PMBCs)

